## B. Research Overlap

We searched the suggested websites using the search terms 'mental health' and 'access,' 'transition,' 'discharge,' 'stepped care' and 'coordination of care' and found no similar studies. Existing studies of care transitions focus on transition into MH treatment, or from inpatient treatment to outpatient SMH. VACO indicated that no similar program exists and reported that only a few sites nationwide had EMR notes for formalizing the transition from SMH to PC but that these were rarely used, had little impact on transitions, and that no incentives or guidance exists to facilitate use. Clinical Practice Guidelines discuss the importance of using stepped care to intensify treatment but do not discuss when or how to transition to less intensive care.

## C. Methods (Evaluation Plan)

**Partnership process.** Partners in VISN 19 originally approached the FLOW team after hearing about the success of FLOW in VISN 17. Initial champions of FLOW in VISN 19 were [name], Deputy ACOS in Eastern Colorado, and [name], Mental Health Director at Rocky Mountain Regional VA. With their enthusiasm about FLOW, they connected our team to the VISN 19 Deputy Chief Medical Officer, [name], and [name], who oversees mental health programs throughout VISN 19. Through a series of calls and emails facilitated by [name], we discussed the mental health priorities of VISN 19 and their current status on SAIL measures and VISN leadership performance metrics. [name] assisted us with obtaining support of VISN leadership, [name]. VISN 19 leadership noted that many of their large facilities struggle with access, with many patients waiting until 14 days or more after their desired date to obtain an appointment. At their request, we provided them with data on how FLOW impacted these metrics when

implemented at Site 1 and provided data on current access metrics in their VISN for comparison. Although all sites expressed interest in participating, 7 sites were able to promise 4 hours per week of protected time for a provider to be the internal facilitator at their sites, with two more tentatively committing. Our partners noted that they were willing to commit to this because they were certain that the financial and time investment “would be returned many times over in freed up FTEE to see new patients in MH” (personal communication, [name], 10/5/18). Project aims were developed in collaboration with VISN 19 to align with their priorities, and methods were tailored to fit their preferences, such as the use of a stepped wedge design.

At the request of VISN 19 we will also provide a less intensive implementation approach to the remaining VISN 19 sites, not included in the 7-9 sites in this project. The other sites will receive a toolkit for implementing FLOW and optional monthly calls for support. This may provide supplemental data regarding whether the intensive implementation approach at the primary 7-9 sites is necessary, or how many sites receiving the scaled down approach are able to implement FLOW. Because the EMR template will be implemented at all VISN 19 facilities, we will obtain data on the number of patients transitioned to primary care throughout VISN 19, regardless of their participation in this program evaluation process. Exploratory, descriptive analyses will compare implementation of FLOW at the 7-9 primary sites to the less intensive implementation sites.

**Study Design Overview.** A cluster-randomized stepped wedge design will examine implementation of FLOW in VISN 19. We chose a stepped wedge (see Table 1) because VISN 19 requested that all participating sites receive the FLOW program, and this design allows balancing of practical considerations with statistical considerations and randomization. This design is also appropriate because we expect the intra-class correlations in sites to be large. We will use the new CONSORT extension for cluster-randomized stepped-wedge trials to report methodological considerations and outcomes. Sites will be matched on resources and staffing ratios and simultaneously randomized to the time in which they begin the intervention (i.e., step 1, 2, or 3) on the basis of matching. Implementation of the program will be examined in three phases. First, data will be collected about the frequency of patient transition during the baseline phase. Next, FLOW will be implemented for 1 year with external and internal facilitation, and program evaluation will be guided by RE-AIM (see Table 1). Finally, there will be a minimum of a 1-year maintenance phase during which only data collection will occur.

**Sites.** Seven to nine VAMCs and very large CBOCs (>10,000 unique patients) from VISN 19 will participate, depending upon final leadership commitment at that time. VISN 19 is the geographically largest in the nation.

**Randomization.** Sites will be randomized based upon balancing relevant characteristics across cohorts. We propose to match upon: facility complexity, staffing ratios in SMH and PC, and PCMHI penetration rate. We will create a composite variable based upon each site’s performance compared to the average participating site. A z-score will be created for each selected variable and averaged to create a final composite variable. Based upon FY19 data, it appears that the three larger VAMCs would be in the higher resource group whereas the smallest VAMC and the 3 very large CBOCs would be in the lower resource group. These calculations will be repeated with the newest data when the study commences and the final number of sites is determined. We will ensure that each cohort in the stepped wedge has 1-2 higher resource sites and 1-2 lower resource sites. If 9 sites participate, we will use a tertile split for matching. A random number generator will be used to assign sites to the step in which they receive the intervention. Sites will be randomized to receive FLOW implementation immediately in sequence 1 or to wait until steps 2 or 3 (see Table 1 for timeline) but will not be informed of their randomization until it is time for the site to begin implementation.

**Table 1. Project timeline.**

Months	Year 1				Year 2				Year 3			
	Q1	Q2	Q3	Q4	Q1	Q2	Q3	Q4	Q1	Q2	Q3	Q4
Startup	X											
Cohort 1 (2 sites)		Implementation				Maintenance						
Cohort 2 (3 sites)			Implementation				Maintenance					
Cohort 3 (2 sites)				Implementation				Maintenance				
Assessment timepoints	●	●	●	●	●	●	●	●	●	●	●	●
Data analysis, papers										X	X	X
Report to VISN leaders	X	X	X	X	X	X	X	X	X	X	X	X

**Pre-implementation data-collection.** Before implementation (i.e., Q1, Q2, or Q3), baseline rates of patient transition from SMH to PC will be examined. Some sites currently have an EMR note template for discharge or transition out of specialty mental health; others document this as needed in medication management session EMR notes. We will use VA administrative databases to identify the pre-FLOW discharge rate. We will also collect assessments of implementation factors tapping the five CFIR domains: intervention

characteristics, outer setting, inner setting, characteristics of individuals, and process.

**Implementation of FLOW.** Implementation of FLOW will occur by implementation facilitation, an evidence-based strategy to change clinical practice, guided by the VA-based implementation facilitation manual. Facilitators partner with key stakeholders to plan change strategies, adapt them to the local context, and address barriers to implementation. Implementation facilitation is a flexible strategy that has been used effectively to create change in VA mental health services. Our multifaceted implementation strategy will use both external facilitation provided by [name], who has received training in facilitation from [name], and internal facilitation provided by a local champion at each site.

As in the pilot, each site will receive FLOW materials and internal and external facilitation, in partnership with a local champion. The process starts with meetings with clinic leadership and identification of a local champion, typically a SMH provider. Sites will be given a list of ideal Internal Facilitator (IF) characteristics (e.g., strong communicator, opinion leader, prior QI or PE experience, well-established in their current position) and will nominate a provider who fits these. Next, the FLOW implementation team meets with providers from the affected clinics: SMH, PCMHI, and PC, to explain the rationale and procedures and answer any questions or concerns. With the input of providers and the local champion, local processes are identified to support communication between different clinics about patients transitioning. Sites are given access to the online FLOW report identifying patients who meet criteria for transition, provider and patient materials to explain the process of transition, and an EMR template with a progress note title to document the transition. The project team initially holds weekly meetings with the local champion to troubleshoot implementation, and implementation is flexibly differentiated to meet each site's identified barriers (see Table 4 for information about strategies employed by facilitators). Data will feed back to the internal facilitator on a monthly basis, including information about both the process of implementation and implementation success. Process data will include barriers and facilitators, types of actions or interventions the IF enacted to overcome barriers or leverage facilitators, assistance from the FLOW team, and local climate and context information arising that affects implementation. Implementation success metrics include the number of patients eligible and transitioned, which providers are engaging in FLOW and which providers have yet to transition any patients, etc. The internal facilitator is responsible for local implementation activities guided by regular calls with the FLOW team.

Although the implementation strategies used are more resource intensive than passive implementation, they are nevertheless more resource efficient than other mental health program implementation efforts in VA such as the evidence-based psychotherapy rollouts and thus likely to be scalable for future national implementation. The primary 'cost' to each facility implementing FLOW is 4 hours per week of one provider's time in the early stages of implementation, with smaller time investment as time goes on. Based upon pilot data, this provides a return on investment of freeing up many hours of specialty mental health provider time to see new mental health patients and substantial improvements in SAIL access metrics.

## Measures/Data Sources

**Outcomes.** Program effectiveness outcomes were developed with VISN 19 leaders and aligned with the RE-AIM framework. VISN 19's priorities are to 1) increase access to timely mental health services for new patients, and 2) ensure that patients who are transitioned back to primary care have a clinically appropriate transition. Considering these priorities, we developed the outcomes discussed in detail in Table 2.

Assessment of implementation factors/determinants and their relationship to FLOW implementation success is guided by the consolidated framework for implementation research (CFIR), which is composed of five major domains: intervention characteristics, outer setting, inner setting, characteristics of the individuals involved, and process. Table 3 shows the proposed implementation factors as aligned with CFIR constructs.

**Table 2. RE-AIM outcomes measured during implementation and maintenance phases (Specific Aim 1).**

RE-AIM Domain	Project Outcome	Measured by:	Level of Analysis	Timepoint
Reach	Patient transition to PC, before and after FLOW implementation	Administrative data for EMR template	Patient	Baseline; quarterly
Effectiveness	Successful patient transition to PC, defined as PCP renews psychotropic prescriptions and patient does not return to SMH within 1 year	VA administrative data for FLOW EMR template use	Patient	Baseline; quarterly in impl. phase
	Patient satisfaction with FLOW	Qual. interviews	Patient	Post-transition
	Provider satisfaction with FLOW	Qual. interviews	Provider	Post-implementation
	Impact on access, measured as (1) gain in provider hours available and (2) gain in % of	CDW Completed Appointments	Provider	Baseline; quarterly

	patients who receive appointments within 7 days of desired date	Cube		
Adoption	Providers who use FLOW for >2 patients Providers' average % of patients engaged If turnover exists, new provider use of FLOW	VA administrative data for FLOW EMR template use	Provider	Quarterly in impl. phase
Implementation	Fidelity in implementation of FLOW components	Implementation checklist	Facility	Monthly
Maintenance	Sustainment, including all RE-AI metrics Continuing facilitation activities taken over by the local facility	All metrics above Assessment of IF behavior	Patient & provider	Quarterly during maintenance phase

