**The FLOW program assists facilities with transitions.** The FLOW program was created to address this need. FLOW consists of EMR-based criteria to identify patients who may be eligible for transition to PC and a user-friendly online report to communicate this information to clinicians. The criteria were developed by the FLOW team in consultation with stakeholders and a Veteran community advisory board. Current criteria are that patients must be taking three or fewer psychotropic medications, not be taking antipsychotics, lithium, or a mood stabilizer when bipolar disorder is present, had no new psychotropic medications in the past 6 months, no psychiatric inpatient or psychiatric ER visits in the past 12 months, and have no suicide risk flag. Recent refinements of these criteria added that the patient must not be taking Suboxone and must not be high risk for suicide based upon REACHVet score. Because these criteria rely upon information available in administrative databases, they may miss subjective signs that the patient is not ready for transition such as milder suicidal ideation or near-hospitalization episodes. As such, provider clinical judgment based upon the individual patient's current functioning, strengths, and resources, is the final determination of eligibility. The process of transition starts first with identification of potential eligibility via the online FLOW report. SMH providers review the list and determine which patients they believe are clinically appropriate, and discuss this with the patient at their next appointment to determine if the patient feels ready to transition. If yes, the SMH provider contacts the PCP to facilitate transition. If a patient is reluctant to transition, the SMH provider may make a plan for what level of functioning would indicate recovery sufficient to transition. FLOW materials discuss how measurement-based care can be used to guide decisions about transition and education materials for providers in SMH and PC about how to have therapeutic conversations with patients about transition. It also contains education materials for patients about the transition, how to address service-connection concerns, what to do if they have a resurgence in symptoms, and an EMR template to document transitions and facilitate communication to PCPs.

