**Implementation phase data collection.** The majority of data during the implementation phase will be collected via VA administrative databases. Use of the FLOW EMR template, extracted from administrative databases, will provide information on reach (% of patients transitioned pre vs. post FLOW implementation), effectiveness (% of patients who receive follow up MH care in PC, based upon filled prescriptions, and % of MH patients who return to SMH, based upon consult and appointment data), and adoption (% of providers using the template at least three times, average rates of transition by provider). We will also track demographic characteristics of transitioned patients to examine whether transition rates differ by gender and ethnic/racial background. CDW clinical/administrative data will also be used to collect information on the impact of FLOW on access by tracking the percentage of all SMH clinic patients who receive an appointment within 0 to 7 days of the preferred date. A second measure of effectiveness will be the expected gain in provider time for new patient appointments as a consequence of transitioned patients. This will be calculated for each provider as # of patients discharged multiplied by the average yearly minutes spent in appointments with a patient. We will also examine impact on provider time available for new patients by tracking the number of completed new patient appointments by provider from pre-post implementation of FLOW.

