**Power analysis.** Power calculations were conducted for the reach and effectiveness outcomes using the Steppedwedge command in Stata Version 14. Although between 7 and 9 sites will participate, power calculations were estimated conservatively, assuming only 6 facilities (clusters) with 2 randomized into each of the 3 steps of the predominately open cohort (i.e., different patients at different timepoints) complete design. Calculations assume a two-tailed alpha of 0.05. VISN 19 leadership reports that few patients are currently being transitioned from MH to PC. Transition rates are <1% of patients in facilities who do not receive the FLOW intervention and between 1-16% of patients in facilities who do receive the FLOW intervention. Given an average of 1000 patients per quarter per facility based upon the Clinic Practice Manager data for VISN 19, a sample size of 6 clusters (24,000 patients in total) achieves 80% power to detect a difference in transition rates from 1% at baseline to 1.65% upon receiving FLOW. Power is >99% to detect a two-fold increase in patients who transition from SMH to PC. Reach, effectiveness, and most maintenance outcomes are binary variables at the patient level (e.g., whether one was transitioned to PC). These outcomes represent an open cohort trial, as different patients will be included at each timepoint within a given site. Adoption outcomes are both binary (e.g., whether a provider engaged in the FLOW process for at least 3 patients) and continuous (e.g., % of patients engaged in FLOW for each provider) at the provider level. These outcomes represent a closed cohort trial, as the same providers will be included at each timepoint. Adequate effectiveness will be declared if at least 90% of transitioned patients successfully transition without return to SMH in the 1 year follow-up period. Given a very conservative estimation that 4% of SMH patients transition from SMH to PC, an average of 40 patients per quarter per facility (4% of 1000 = 40), a sample size of 6 clusters (960 transitions in total) will allow for 80% power to detect a difference in the percentage of patients who successfully transitioned to primary care from 76.50% to 90% upon receiving FLOW.

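### A psychiatric admission, psychiatric ER visit, new suicide-risk flag or death after transition is scored a success if the prescription was renewed and no SMH consult or appointment follows within the year

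*Combined protocol and SAP*

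**What the plan says.** Table 2 (Effectiveness row) gives success two conditions and no others: "Successful patient transition to PC, defined as PCP renews psychotropic prescriptions and patient does not return to SMH within 1 year". The Implementation phase data collection paragraph says how each is measured. Primary care follow-up is the percentage "of patients who receive follow up MH care in PC, based upon filled prescriptions", and return is the percentage "of MH patients who return to SMH, based upon consult and appointment data".

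The Power analysis paragraph sets the decision rule: "Adequate effectiveness will be declared if at least 90% of transitioned patients successfully transition without return to SMH in the 1 year follow-up period". That sentence spells out only non-return and does not mention the renewal condition.

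The FLOW description in section A lists, among the eligibility criteria, "no psychiatric inpatient or psychiatric ER visits in the past 12 months, and have no suicide risk flag". It introduces a limitation of the criteria with "Because these criteria rely upon information available in administrative databases", so these items can be obtained without new data collection. Under Measures/Data Sources, VISN 19's second priority is to "ensure that patients who are transitioned back to primary care have a clinically appropriate transition", and the outcomes are said to have been developed with that priority in view.

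**The concern.** The plan treats a psychiatric admission or ER visit in the year before transition, and a suicide-risk flag at transition, as signs that a patient is not a candidate. In the year after transition it does not look at them. Follow-up is where a poor selection would show, and section A itself concedes that the administrative criteria can miss patients who are not ready.

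Two things are at stake. First, the 90% criterion could be met in part by patients whose course was the opposite of a clinically appropriate transition. Second, whatever happens to that criterion, the evaluation would have no count of serious psychiatric events or deaths among transitioned patients, although its results are meant to inform a national rollout.

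**Working it through.** **1. How each event is scored under the current wording.** All cases assume no SMH consult or appointment in the rest of the year.

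| Event after transition | Table 2 definition | 90% rule as worded in Power analysis |
|---|---|---|
| Psychiatric admission or ER visit, prescription renewed | Success, unless the encounter itself is read as a return (not stated) | Success, same caveat |
| New suicide-risk flag, prescription renewed | Success | Success |
| Death after a renewal | Success | Success |
| Death before any renewal | Not a success | Success, because only non-return is named |

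If an SMH consult or appointment does follow within the year, the patient is a failure in every row. The gap is therefore limited to events with no such contact.

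**2. The plan's own power figure.** The inputs come from Power analysis: 6 clusters, 3 steps (hence 4 periods), 40 transitions per cluster-quarter, 76.5% versus 90%, and "Calculations assume a two-tailed alpha of 0.05". The ICC values of 0.10 to 0.25 are in the paragraph that follows. I used the Hussey-Hughes variance with binomial variance at the baseline rate:

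- v = 0.765 × 0.235 = 0.1798. At ICC 0.10, τ² = 0.01798 and σ² = 0.9 × 0.1798 / 40 = 0.004045.
- With I = 6, T = 4, U = 12, W = 56 and V = 28: Var = Iσ²(σ² + Tτ²) / [(IU − W)σ² + (U² + ITU − TW − IV)τ²] = 6 × 0.004045 × 0.07595 / (16 × 0.004045 + 40 × 0.01798) = 0.00235, so SE = 0.0485.
- Power = Φ(0.135 / 0.0485 − 1.96) = 79.5%. At ICC 0.15, 0.20 and 0.25 it is 81.3%, 83.3% and 85.5%.

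The stated 80% reproduces. The issue is the definition of the outcome, not the arithmetic.

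**3. The denominator for the 90% rule.** 6 × 4 × 40 = 960 transitions in all. Of the 24 cluster-quarters, 12 are FLOW-exposed, so 12 × 40 = 480 bear on the rule, and 432 of 480 is exactly 90%.

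**4. Patients misclassified.** The documents give no event rate. I assume 1%, 2%, 3% or 5% of transitioned patients have an event with no SMH contact afterwards. Then 480 × rate gives about 5, 10, 14 and 24 patients, and success is overstated by 1, 2, 3 and 5 points.

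**5. When the decision changes.** The chance of at least 432 successes in 480 once the events count as failures (binomial, clustering ignored):

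| Rate under current definition | 0% hidden | 1% | 2% | 3% | 5% |
|---|---|---|---|---|---|
| 92% (illustration only) | 95% | 80% | 54% | 27% | 3% |
| 95% (illustration only) | ~100% | ~100% | 99% | 95% | 54% |
| 97.8% (pilot return rate, all renewed) | ~100% | ~100% | ~100% | ~100% | 99% |

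The last row uses 9 / 411 = 2.2% returning in the pilot (section A), so 100 − 2.2 = 97.8%. Hidden events would have to reach 97.8 − 90 = 7.8% before the inclusive rate fell below 90%.

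**6. What the interviews could show.** About 45 Veterans and 27 providers are planned. At 1-5%, the expected number of affected Veterans among 45 is 0.45 to 2.25, and those who died cannot be interviewed.

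**The case against.** The strongest reply is that the 1-year window already catches much of this. An admission, an ER visit or a new flag would often lead to an SMH consult or appointment, and any such contact makes the patient a failure. That stands. A reader might infer that every psychiatric admission or ER visit after transition is scored a success; the documents do not support that. They leave open whether the encounter itself counts as a return, and they catch any later SMH contact.

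The size is also open to challenge. Candidates are screened for recent admissions, ER visits, flags and high REACHVet risk, and then by clinical judgment. The assumed 1-5% covers only events without SMH contact, whereas all returns in the pilot were 2.2%. The upper end may well be high. The pilot comparison is itself only illustrative, because the pilot's follow-up length and renewal rate are not given.

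The interviews do ask Veterans and providers whether transitions were appropriate, so the second priority is not ignored. With these numbers, however, they cannot estimate the rate of uncommon serious events.

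Finally, an unrelated death says nothing about whether a transition was suitable, so counting every death as a failure is not clearly right. That stands too, and the fix allows for it. None of this answers the core point: the plan does not say how these events are handled, and nothing it lists would count them.

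**Conclusion.** The point holds as a gap in the outcome definition. As written, an admission, ER visit, new flag or post-renewal death with no later SMH consult or appointment is scored a success, and no quantitative outcome records it. Under an assumed 1-5% of about 480 FLOW-exposed transitions, that is 5-24 patients and 1-5 points. The 480 follows the plan's conservative six-site layout with 40 transitions in every cluster-quarter; the shift in percentage points does not depend on it.

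It would be tempting to conclude that the 90% criterion will be met falsely. The documents do not support that: the decision changes only if the observed rate is within the hidden-event margin of 90%, and on the pilot's return figure with all prescriptions renewed that margin is about 7.8 points. The lack of event reporting does not depend on any assumed rate, and is reason enough to change the plan. The finding rests on the text supplied; the appendices were not included.

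**What to change.** - In Table 2, the Implementation phase data collection paragraph and the Power analysis paragraph, count a psychiatric inpatient stay or psychiatric ER visit within 1 year of transition as not a successful transition.
- State how a new suicide-risk flag and death are handled, for example death as a separately reported competing event rather than a success.
- Report each event separately for all transitioned patients, before and after FLOW, explicitly including those discharged from SMH. Use the administrative sources behind the eligibility criteria. Death is not among those criteria, so name its source.
- Bring the wording of the 90% rule into line with Table 2, including the renewal condition.
- Keep the return-only percentage alongside, so that comparison with the pilot is preserved.

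The cost is one added data query, revised outcome wording and a slightly lower success percentage. If the events are equally common before and after FLOW, power at ICC 0.10 falls from 79.5% to 78.4%, 77.3%, 76.3% and 74.4% at 1%, 2%, 3% and 5%. If they occur only under FLOW it falls to 73.2%, 66.0%, 58.1% and 41.8%, but that reflects a smaller real benefit, which the evaluation should be able to show.
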